- ISGA will be collected via skin examination to evaluate efficacy of Crisaborole 2% topical ointment in the treatment of seborrheic dermatitis. A 0 or 1 (clear or almost clear) on the ISGA would be considered a treatment success

Secondary Outcome Measure:

- The Itch NRS will be collected to assess the percentage of improvement of patient reported itching. This will be calculated as a percent changes from baseline in the Itch NRS scale.

Safety Outcome Measures

- Incidence, severity, and type of treatment-emergent adverse events will be collected via the local tolerability assessment
- Vital signs, clinical assessments, and laboratory test results
- Concomitant medication use
- Adverse events

Primary Objective

- To assess the efficacy of crisaborole ointment 2% (Eucrisa) in the treatment of mild to moderate seborrheic dermatitis.

Statistical Analysis

As this is a proof of concept, open label study, descriptive statistics will be utilized. The goal is for the information to yield data points robust enough to be accepted in a high impact, peer reviewed journal. The sample size was based known patient population and pragmatic considerations and is adequate to characterize anticipated observed effects.

Study Design

40 eligible subjects will be enrolled

Inclusion criteria

1. Capable of understanding and willing to provide signed and dated written voluntary informed consent before any protocol specific procedures are performed.
2. Male or female subjects 18 to 70 years of age.
3. Able to complete the study and to comply with study instructions.
4. Female subjects of childbearing potential must have a negative pregnancy test. Sexually active women of childbearing potential participating in the study must agree to use a medically acceptable form of contraception (which includes oral contraception, injectable or implantable methods, or intrauterine devices) during the entire duration of the study
5. Mild to moderate seborrheic dermatitis on the face with an ISGA of 2 or 3 at baseline.

Exclusion criteria

1. Use of systemic antifungal agents, corticosteroids or other immunosuppressive therapies, or systemic retinoids within 4 weeks prior to the baseline visit.

2. Use of topical antifungal therapy, corticosteroid therapy, or calcineurin inhibitors to the face, within 2 weeks prior to the baseline visit. Topical, over-the-counter antifungal shampoo will be allowed as long as it has remained constant for 4 weeks prior to baseline.

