3. Use of any investigational drugs within 4 weeks prior to the baseline visit, or subjects scheduled to receive an investigative drug other than the study product during the period of the study.
4. History of known or suspected intolerance to any of the ingredients of the study product.
5. Female subjects who are pregnant, trying to become pregnant or lactating.
6. Any clinically relevant abnormal vital signs or findings on the physical examination which in the opinion of the investigator might interfere with the study assessments.
7. A clinically relevant history of abuse of alcohol or other drugs.
8. Any major illness within 30 days prior to the baseline visit.
9. Subjects with any clinically significant condition which would, in the opinion of the investigator, compromise the subject's participation in the study.
10. Subjects who are immunocompromised (ex: HIV).
11. Considered unable or unlikely to attend the necessary visits.
12. Currently using any medication, which in the opinion of the investigator may affect the evaluation of the study product
13. Subjects who have significant neurological conditions (Parkinson's disease or Stroke), who in the opinion of the investigator are not eligible for the study due to the severity of neurological condition.
14. Subjects with a history of non-melanoma skin cancer of the face within 6 months

Procedures:

After the informed consent process, the subject will be evaluated for facial seborrheic dermatitis utilizing the Investigator's Static Global Assessment (ISGA). The subject must have a ISGA score of 2 or 3 to qualify for the study.

Patient reported outcomes will be collected at baseline and week 4. We will utilize the SkinDex29 and Itch NRS.

Provider and Patient local tolerability assessment will be collected at Baseline (before medication application) week 1, 2, and 4. We will assess for redness, pain, burning, and scaling at the application site.

Adverse events will be collected from after the informed consent document is signed through week 4.

Concomitant medications will be collected from screening to week 4.

Subjects can continue to use their over-the-counter dandruff shampoo as long as it has remained constant for the past 4 weeks. Subjects will be instructed to avoid the facial area with the shampoo.

Subjects may continue their established makeup, moisturizer and sunscreen regimen.

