Other than Urine Pregnancy Tests for women of childbearing potential, no other laboratory evaluations are necessary.

Patients will be instructed to apply a thin layer of medication to the affected area on the face twice daily for 4 weeks, and they will be advised that the medication is not for ophthalmic, oral, or intravaginal use.

Procedures are listed in table below.

Schedule of Events

	Scr	BL	Wk1	Wk 2	Wk 4
Informed Consent	x				
Inclusion/Exclusion Criteria	x	x			
Med History	x				
PE	x				x
Investigator Static Global Assessments (ISGA)	x	x	x	x	x
Seborrheic dermatitis grading scale	x	x	x	x	x
Photography	x	x	x	x	x
UPT	x				x
Con Meds	x	x	x	x	x
AE		x	x	x	x
SkinDex 29		x			x
Itch NRS		x			x
Patient and Provider Tolerability Assessment		x	x	x	x

ⁱ Katsambas A, Antoniou C, Frangouli E, Avgerinou G, Michailidis D, Stratigos J. A double-blind trial of treatment of seborrheic dermatitis with 2% ketoconazole cream compared with 1% hydrocortisone cream. *Br J Dermatol*. 1989 Sep;121(3):353–7.

ⁱⁱ Piérard-Franchimont C, Piérard GE, Arrese JE, De Doncker P. Effect of ketoconazole 1% and 2% shampoos on severe dandruff and seborrheic dermatitis: Clinical, squamometric and mycological assessments. *Dermatology*. 2001;202(2):171–6.

ⁱⁱⁱ Stratigos JD, Antoniou C, Katsambas A, Böhler K, Fritsch P, Schmölz A, et al. Ketoconazole 2% cream versus hydrocortisone 1% cream in the treatment of seborrheic dermatitis. A double-blind comparative study. *J Am Acad Dermatol*. 1988 Nov;19(5 Pt 1):850–3.

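### Minor safety point: eligibility is re-checked at baseline, but the urine pregnancy test is scheduled only at screening and Week 4, so treatment may start without a test at first dose if the two visits fall on different days

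*Combined protocol and SAP*

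**What the plan says.** Inclusion criterion 4 requires that "Female subjects of childbearing potential must have a negative pregnancy test". It adds that sexually active women in this group "must agree to use a medically acceptable form of contraception" for the whole of the study. Exclusion criterion 5 bars "Female subjects who are pregnant, trying to become pregnant or lactating".

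The Schedule of Events has separate columns for screening (Scr) and baseline (BL), followed by Weeks 1, 2 and 4. The inclusion/exclusion row is marked at Scr and BL. The urine pregnancy test (UPT) row is marked at Scr and Wk 4 only.

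The Procedures section allows no other laboratory check that could fill the gap: "Other than Urine Pregnancy Tests for women of childbearing potential, no other laboratory evaluations are necessary". It places a pre-treatment assessment at baseline: "Provider and Patient local tolerability assessment will be collected at Baseline (before medication application) week 1, 2, and 4". Subjects are then told to "apply a thin layer of medication to the affected area on the face twice daily for 4 weeks".

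Nothing in the document limits the time between Scr and BL, says that they occur on one day, or asks for a pregnancy test before the first application.

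**The concern.** The protocol makes pregnancy a bar to treatment and checks eligibility twice, the second time at the visit where treatment begins. The only objective evidence on pregnancy is collected at the first of those checks. At the second, a site following the schedule as written can confirm criterion 4 and exclusion 5 from the screening result and the subject's history.

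The other criterion that can change between visits is handled differently. Inclusion criterion 5 requires "Mild to moderate seborrheic dermatitis on the face with an ISGA of 2 or 3 at baseline", and the ISGA is measured again at BL. Pregnancy status can also change between visits, but its test is not repeated there.

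What is at stake is participant safety: whether non-pregnancy is verified when exposure starts. The ISGA outcome and the descriptive analysis are not involved.

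**Working it through.** The plan states no figure to reproduce. The check is a row-by-row reading of the Schedule of Events, followed by a simple expression for the age of the test.

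**Step 1: the relevant rows.**

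| Row | Scr | BL | Wk1 | Wk 2 | Wk 4 | Marked |
|---|---|---|---|---|---|---|
| Inclusion/exclusion | x | x | | | | 2 of 5 |
| ISGA | x | x | x | x | x | 5 of 5 |
| UPT | x | | | | x | 2 of 5 |
| Tolerability | | x | x | x | x | 4 of 5 |

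The empty BL cell for UPT does not look like a fault of text extraction. The physical examination row has the same pattern (Scr and Wk 4), and rows that begin at BL, such as adverse events and Itch NRS, correctly show a blank Scr cell.

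**Step 2: when treatment starts.** Tolerability is recorded at BL before medication is applied, and the Scr column has no tolerability mark. The first application is therefore at or after BL.

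**Step 3: age of the last scheduled test at first dose.** Let S be the number of days from Scr to BL, and A the age of the last scheduled test at first dose. Since the first dose is at or after BL, A ≥ S. The documents do not give S, so every value below is an assumption.

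- S = 0 (both visits on one day): A ≥ 0. The screening test is also a baseline test, and there is no gap.
- S = 14: A ≥ 14 days. This would describe a subject who stops a facial topical drug on the day of screening and waits until exclusion 2 no longer applies ("Use of topical antifungal therapy, corticosteroid therapy, or calcineurin inhibitors to the face, within 2 weeks prior to the baseline visit").
- S = 28: A ≥ 28 days. This is the same hypothetical with a systemic drug under exclusion 1, whose look-back is 4 weeks (4 × 7 = 28).

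The values 14 and 28 are look-back windows used for illustration. They are not visit intervals taken from the plan. No upper limit on S is stated.

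**Step 4: is S > 0 realistic?** Three features make it plausible. Screening and baseline have separate columns; ISGA, the grading scale, photography, concomitant medications and eligibility are marked in both; and exclusions 1 to 3 count back from the baseline visit rather than from consent. None of these proves that the visits are on different days.

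**Step 5: the next scheduled test.** After Scr it is at Wk 4, when the 4-week course is ending. If S > 0, no scheduled test falls between screening and the end of treatment.

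**The case against.** The best reply is that the gap depends on a condition the documents do not show. The Procedures text describes no distinct screening visit: after consent, the ISGA is done and must be 2 or 3 to qualify, and criterion 5 refers to that score at baseline. This fits same-day visits. The objection stands as far as it goes, and the point is therefore stated conditionally.

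A second reply is that safeguards already cover the interval. Contraception is required for the whole study, not only during dosing, and exclusion 5 is among the criteria checked again at BL. These lower the risk. But the contraception clause is an agreement and applies only to sexually active women, and a re-check of exclusion 5 without a test rests on history. Neither verifies status at first dose. An investigator may of course repeat the test, but nothing requires it.

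A third reply is that the plan already accepts the treatment period without an interim test, so a similar gap before treatment should be tolerable. There is some force in this, and it is one reason to rate the point as minor. The two situations do differ: confirming that an entry criterion is met when treatment starts is a separate matter from monitoring during it.

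Stronger readings are tempting but not supported:

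- A reader might infer that women would be treated on an expired test. The documents give no validity period, so they show only that a test may be S days old.
- A reader might take 14 or 28 days as the typical gap. The plan describes no washout procedure, and since eligibility is also checked at Scr, a site could decline to proceed with such a subject.
- A reader might infer a count of exposed pregnancies or a fetal risk. The documents support no estimate of either.

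**Conclusion.** The point holds as a minor, optional safety improvement. The schedule facts are firm: UPT at Scr and Wk 4 only, eligibility at Scr and BL, and no stated limit on the interval between them. The consequence is conditional. If the visits fall on different days, a woman of childbearing potential can begin treatment with no test at first dose; if they coincide, there is no gap.

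The size cannot be given beyond A ≥ S with S unknown. The documents do not say how many subjects would have S > 0 or how many of the 40 planned subjects are women of childbearing potential. The conclusion assumes that the first application is at or after BL, as the timing of the tolerability assessment implies. It has no bearing on the efficacy analysis.

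**What to change.** Mark UPT at BL in the Schedule of Events, with the result read before study product is dispensed. One test serves both visits if they are on the same day. Alternatively, move the Scr test to BL. In either case keep the Wk 4 test.

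**Cost.** Adding the test changes one schedule cell and means about one extra urine test per woman of childbearing potential who reaches BL on a different day from Scr. The visit is already held, and it already includes an assessment that precedes application, so its order need not change. The enrolment target of 40 should not be read as a strict ceiling on extra tests, because a woman who tests positive at BL would be tested but not treated. Moving the test adds none, but an occasional screen failure would be found one visit later.

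A stated maximum Scr-to-BL interval, or a same-day rule, would also limit the age of the test, at the price of less flexible scheduling. A very recent conception can still be missed under any of these options.
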